5.2 Dosage and Administration

Phase 1 Portion

The pamiparib will be taken once on Day 1 of Cycle 1 (morning only), followed by a 1-day treatment-free period (Day 2). Regular daily administration of pamiparib will commence on the morning of Day 3 of Cycle 1, as a 21-day period of repeated drug administration (Days 3 to 23). During subsequent cycles, the patients will take pamiparib BID from Day 1 to Day 21 (with no treatment-free or rest period).

Patients will be required to fast for at least 2 hours before and 1 hour after each administration of pamiparib throughout the study.

Phase 2 Portion

The patients will take pamiparib at 60 mg BID daily from Day 1 of Cycle 1 (with no treatment-free or rest period). Pamiparib capsules will be administered PO BID, once in the morning and once in the evening. The time difference between two consecutive doses will be approximately 12 hours with a window of ± 4 hours. Patients will be instructed to swallow the capsules whole, in rapid succession, with water. Pamiparib can be administered with or without food. However, to reduce gastrointestinal irritation that parmiparib may cause, patients are encouraged to take parmiparib with food.

A dose of pamiparib should be skipped if it is not taken within the upper range of the scheduled time, ie, within 16 hours. An extra dose of pamiparib should not be taken to make up for a missed dose. If vomiting occurs during the course of treatment, no re-dosing of the patient is allowed before the next scheduled dose.

On days with PK assessments, the morning dose of pamiparib should be administered in the clinic in accordance with the schedule for the PK samples.

The toxicity-related treatment delay must be agreed upon by the investigator and the sponsor Medical Monitor.

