5.2.1 Treatment interruption and treatment discontinuation

All dose modifications should be based on the worst preceding toxicity. Generally, all dose interruptions or treatment discontinuation will be based on investigational drug-related AEs. For

reasons other than drug-related AEs, eg, safety concerns due to the poor health condition, if deemed necessary by the investigators, dose modifications could be applied after discussion with medical monitor.

Each patient is only allowed up to 2 dose reductions. In addition, a patient must discontinue treatment with pamiparib if, after treatment is resumed at a lower dose, the toxicity recurs with the same or worse severity.

Toxicity		Recommended Dose Modification ^a			
Hematologic					
Anemia (hemoglobin, Hgb)					
Hgb < 9.0 g/dL		 First occurrence of Hgb < 9.0 g/dL: Hold pamiparib and treat as medically indicated to get Hgb to ≥ 9 g/dL, and then ↓ pamiparib by 1 dose level to 40 mg BID 			
Grade 2 (8 ≤ Hgb <10	$9 \le Hgb < 10$ g/dL	• Continue dosing at current dose level and treat with appropriate supportive care as medically indicated			
g/dL)	$8 \le Hgb < 9 g/dL$	 Subsequent occurrence following dose reduction for anemia: Continue pamiparib without interruption with appropriate supportive care based on clinical assessment OR Hold pamiparib and treat as medically indicated to get Hgb to ≥ 9 g/dL, then restart at reduced dose level OR Hold pamiparib and treat as medically indicated to get Hgb to ≥ 9 g/dL, then √ pamiparib by 1 additional dose level to 20 mg BID 			
Grade 3 (Hgb < 8 g/dL)		 Subsequent occurrence following dose reduction for anemia: Continue pamiparib without interruption with appropriate supportive care based on clinical assessment OR Hold pamiparib and treat as medically indicated to get Hgb to ≥ 9 g/dL, then restart at reduced dose level OR Hold pamiparib and treat as medically indicated to get Hgb to ≥ 9 g/dL, then √ pamiparib by 1 additional dose level to 20 mg 			

BID

Table 9.	Criteria for interruption and re-initiation of Pamiparib due to treatment
associated ad	verse event

Toxicity	Recommended Dose Modification ^a

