Grade 4 (life-threatening consequences; urgent intervention indicated)	 Second occurrence following dose reduction for anemia: Hold pamiparib and treat as medically indicated to get Hgb to ≥ 9 g/dL, then ↓ pamiparib by 1 additional dose level to 20 mg BID Third occurrence following 2 dose reductions for anemia: Discontinue pamiparib if anemia is not caused by any other confounding event, eg GI hemorrhage. Hold pamiparib and treat as medically indicated to get Hgb to ≥ 9 g/dL, then restart at reduced dose level.
 higher anemia, hematolog 2) For any patients showing explanation such as gastro 3) Dose increase can be considered 	should be done for the first 3 cycles during the study. For all Grade 2 or gy test should be done weekly thereafter until adequate recovery. Hgb dropping > 2 g/dL especially within a short time without alternative pointestinal bleeding, ψ pamiparib by 1 dose level should be considered sidered in certain cases, depending on approval from the medical monitor, naintained above 9 g/dL for at least 3 months
Neutropenia (absolute neutroph	il count, ANC)
Grade 3 (ANC <1.0 - 0.5 × 10 ⁹ /L)	 Hold pamiparib until resolved to Grade ≤2 or baseline If resolved ≤7 days, then maintain dose levels If resolved >7 days, then ↓ pamiparib by 1 dose level
Grade 4 (ANC $< 0.5 \times 10^{9}/L$)	Hold pamiparib until resolved to Grade ≤ 1 or baseline and ψ pamiparib by 1 dose level
Febrile neutropenia (ANC $<1.0 \times 10^{9}$ /L with single temperature of >38.3°C or sustained temperature of \geq 38°C for >1 hour)	Hold pamiparib until resolved and ↓ pamiparib by 1 dose level
Thrombocytopenia (platelet cou	unt, PLT)
Grade 3 (PLT <50 - 25 × 10 ⁹ /L)	 Hold pamiparib until resolved to Grade ≤1 or baseline If resolved ≤7 days, then maintain dose levels If resolved >7 days, then ↓ pamiparib by 1 dose level
Grade 4 (PLT $<25 \times 10^{9}/L$)	Hold pamiparib until resolved to Grade ≤1 or baseline and ↓ pamiparib by 1 dose level

Toxicity	Recommended Dose Modification ^a			
Renal				
Estimated glomerular filtration rate (CKD-EPI EQ; Appendix 6)				
If $\geq 60 \text{ mL/min}/1.73 \text{ m}^2$ at baseline: <30 to 15 mL/min/1.73 m ² or If <60 mL/min/1.73 m ² at baseline: $\geq 50\%$ reduction from baseline	 Hold pamiparib until resolved to ≥60 mL/min/1.73 m² If resolved ≤7 days, then maintain dose levels If resolved >7 days, then ↓ pamiparib by 1 dose level 			
Regardless of baseline: <15 mL/min/1.73 m ²	Permanently discontinue pamiparib			
Hepatic				
Bilirubin				

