# 4.2.2 Secondary Endpoints

- DOR is defined as the time from the first determination of a confirmed overall response until
  the first documentation of progression or death, whichever comes first
- PFS is defined as the time from first dose of study medication to the first documented disease progression or death due to any cause, whichever occurs first
- OS is defined as the time from the first dose of study medication to the date of death due to any cause

Version 1.1: 02/28/2020 Page 9 of 28

- ORR as defined above in advanced HGOC patients by investigator review
- CA-125 response rate per GCIG criteria for CA-125 changes
- Incidence of AEs, overall and by severity, and incidence of SAEs; laboratory abnormalities; changes in laboratory assessments, ECGs, and assessment of physical examinations such as vital signs
- For patients participating intensive PK sample collection: AUC,  $C_{max}$ , and  $T_{max}$ ;  $t_{1/2}$ , CL/F,  $V_z/F$
- DCR and CBR as defined above

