# 6.2.2 Conventions

Unless otherwise specified, the following conventions will be applied to all analyses:

- 1 year = 365.25 days. Number of years is calculated as (days/365.25) rounded up to 1 significant digit.
- 1 month = 30.4375 days. Number of months is calculated as (days/30.4375) rounded up to 1 significant digit.
- Age will be calculated as the integer part of (date of informed consent date of birth + 1)/365.25
- P-values will be rounded to 4 decimal places. P-values that round to 0.0000 will be presented as '< 0.0001' and p-values that round to 1.000 will be presented as '> 0.9999'.
- Time-to-event or duration of event endpoints will be based on the actual date the radiograph was obtained rather than the associated visit date.
- Missing efficacy or safety data will not be imputed unless otherwise specified.
- For laboratory results collected as < or >, a numeric value, 0.0000000001 will be subtracted or added, respectively, to the value.
- For by-visit observed data analyses, percentages will be calculated based on the number of patients with non-missing data as the denominator, unless otherwise specified.

**Version 1.1**: 02/28/2020 Page 11 of 28

• For continuous endpoints, summary statistics will include n, mean, standard deviation, median, Q1, Q3 and range (minimum and maximum).

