#### 6.7 AD HOC ANALYSES

Protocol version 5.0 was released on 21 September 2018, which was in the middle of study conduct. The new version of the protocol was mainly aiming to provide more proactive dose modification algorithm and closer hematology monitoring in early stage of drug administration in order to improve the hematological safety management.

The analysis of hematological safety data comparison of pamiparib between pre- and post-protocol amendment (PA) for patients in phase 2 is proposed. Post-PA subgroup is defined as patients signed the first ICF under protocol version 5.0 and Pre-PA subgroup includes patients who signed ICF under at least one previous protocol version. The detailed description of the analysis is in Appendix 10.2.

As a consequence of dose reduction, a proportion of patients will end up with lower dose levels, other than the starting dose level, for their rest of treatment. An analysis of ORR, DCR, CBR, TTR, DOR and PFS will be summarized by most recent prescribed dose level (60mg, 40mg and 20mg) by IRC for PSOC patients in phase 2.

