# C3. Extent of Exposure and Dose Modification

The following measures of overall extent of study drug exposure in patients between pre- and post-PA will be summarized:

• Duration of treatment (months), defined as (earlier of date of last nonzero dose and data cutoff date – date of first dose + 1) / 30.4375

**Version 1.1**: 02/28/2020 Page 27 of 28

- Number (%) of patients in each treatment duration category
- Number (%) of patients with dose modification (interruption and reduction)
- Number (%) of patients with dose interruptions and reasons of dose interruptions
- Number (%) of patients with dose reductions and reasons of dose reductions
- Time to first dose reduction (weeks), defined as (earlier of date of first nonzero dose date date of first dose + 1) / 30.4375 for patients with dose reduction

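### Two descriptive ad hoc analyses in the SAP need correcting: time to first dose reduction contains no reduction date, and efficacy by most recent dose groups patients by their post-baseline dose history

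*SAP*

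**What the plan says.** **Time to first dose reduction.** SAP Appendix 10.2, C3, lists "Time to first dose reduction (weeks), defined as (earlier of date of first nonzero dose date" and then the date of first dose, plus 1, all divided by 30.4375, for patients with a reduction. SAP 6.2.2 gives that divisor its meaning: "1 month = 30.4375 days".

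**Efficacy by dose.** SAP 6.7 observes: "As a consequence of dose reduction, a proportion of patients will end up with lower dose levels". It then plans that six endpoints (ORR, DCR, CBR, TTR, DOR, PFS) "will be summarized by most recent prescribed dose level (60mg, 40mg and 20mg) by IRC for PSOC patients in phase 2". It names no landmark or time-dependent method and gives no caveat. SAP 6.2.4 plans no covariate adjustment.

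**The rules that decide who lands in which group.**
- Starting dose, Protocol 5.2, Phase 2: "The patients will take pamiparib at 60 mg BID daily from Day 1 of Cycle 1".
- Reductions, Protocol 5.2.1: "Each patient is only allowed up to 2 dose reductions". No time window is stated.
- Protocol 4.1.2.1: treatment ends at disease progression.
- Re-escalation, notes to Protocol Table 9: an increase can be considered "in certain cases, depending on approval from the medical monitor" once hemoglobin has stayed above 9 g/dL for at least 3 months. The table footnote also leaves re-escalation open.
- SAP 4.2.2: "PFS is defined as the time from first dose of study medication".

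**The concern.** Both dates in the C3 line are the date of first dose, so the result cannot depend on when a reduction happened. The label and the divisor also disagree on the unit.

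In SAP 6.7 the grouping variable is known only after follow-up. A patient must remain on treatment long enough to be reduced, and again to be reduced twice. A patient who progresses at the first scan without an earlier reduction is counted at 60 mg whatever would have happened later. A patient who reaches 20 mg brings along the progression-free time already spent at 60 and 40 mg, and any response first seen there.

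The table bears on a question that readers will ask: does reducing the dose cost efficacy? Longer PFS or higher ORR at 40 or 20 mg could be taken as reassurance when part of it reflects who stayed on treatment.

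**Working it through.** **The plan's own figure.** The ad hoc sections state none. The related planning figure, the primary test (80 patients, 30% versus 52%, one-sided 0.025, SAP 5 and 6.4.1), reproduces: 33 responders are needed, exact alpha is 0.0211 and power is 0.979, against the stated 98%. Nothing below touches it.

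**C3 formula.** The operator between the two dates is missing from the text as read. I take it as a minus, as in the treatment-duration line of the same list, and do not count it as an error.
- As written: (first dose − first dose + 1)/30.4375 = 1/30.4375 = 0.033 for every patient with a reduction.
- Date corrected, divisor kept, reduction at 56 days by this count: 56/30.4375 = 1.84, under a weeks label.
- Both corrected: 56/7 = 8.0 weeks.

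**Grouping by last dose.** The simulations use 400,000 patients per scenario with no dose effect. Assumptions: exponential PFS; follow-up uniform from 12 to 24 months (the SAP's 12 months after the last first dose, plus an assumed 12 months of accrual). In the lead case 40% of patients are prone to each reduction step, with a median of 1.5 months per step, independent of PFS. Kaplan-Meier median PFS by last dose, at overall median 9 months unless stated:

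| Scenario | 60 mg | 40 mg | 20 mg |
|---|---|---|---|
| Lead case, overall median 6 | 5.0 | 7.0 | 9.7 |
| Lead case | 7.8 | 9.9 | 13.0 |
| Lead case, overall median 12 | 10.8 | 13.0 | 15.9 |
| All reductions within 9 weeks | 8.4 | 9.7 | 10.6 |
| Lead case, 30% re-escalated | 8.3 | 9.8 | 11.9 |
| Lead case, 60% re-escalated | 8.8 | 9.6 | 9.8 |
| Lead case, 90% re-escalated | 9.1 | 9.5 | 6.1 |
| Lead case, reduction-prone patients at PFS hazard ratio 1.33 | 8.7 | 8.5 | 11.5 |
| All within 6 weeks and hazard ratio 1.33 | 9.6 | 8.0 | 8.7 |

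Re-escalation here means one level up after 3 months at the reduced dose. In the hazard-ratio rows the overall median is held at 9 months.

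The gap between 60 and 20 mg is therefore 13.0 − 7.8, about 5 months, in the lead case and 10.6 − 8.4, about 2 months, with all reductions inside 9 weeks. Later reductions widen it: at constant risk with a 6-month median per step it is 14.1 months.

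**Other endpoints, lead case at median 9.** Overall ORR is set to 52%, with first response at week 6, 12 or 18 in 60/25/15% of responders. The 60-versus-20 mg gaps are 14 points in ORR, 13 in DCR, 22 in CBR and 1.9 months in median DOR. Mean TTR differs by 0.05 months.

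**A second set of assumptions.** This follows the protocol scan schedule, lets responders progress later than non-responders and gives an overall median PFS of 8.3 months. With a mean of 40 weeks to first reduction, ORR is 35/60/77% and PFS 4.1/10.3/17.5 months for 60/40/20 mg. With all first reductions inside 6 weeks, 60 and 40 mg are about equal (ORR 52% and 51%, PFS 8.3 months in both).

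**The case against.** **Direction.** A reader might infer that the table must flatter the reduced doses. The documents do not support that. It holds if reduction is unrelated to prognosis and not confined to the first weeks. Patients who need reductions may be frailer; the hazard-ratio rows show the 40 mg advantage disappearing and, with early reductions, the order reversing. Early reductions are plausible, because SAP 6.7 describes protocol version 5.0 as bringing more proactive dose modification and closer early hematology monitoring. Frequent re-escalation works the same way. This objection stands, and it makes direction and size conditional.

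**Size.** The two sets of assumptions give ORR gaps of 14 and 42 points, so no single figure should be quoted as the bias. The lead case also uses continuous progression times; its DOR gap of 1.9 months is shorter than one 9-week scan interval. This too stands.

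**Importance.** SAP 6.7 only summarizes: there is no test and no claim that reduction preserves efficacy. Hypothesis testing is confined to ORR in platinum-sensitive patients. A footnote would meet part of the concern, but medians shown side by side by dose invite comparison.

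**The C3 line.** A reader might infer that the output will be wrong. That is not known. The single date after the word earlier points to a drafting slip from the treatment-duration line, the intent is clear, and SAP 10.1 and 10.3 refer to a separate derivation document not available here. The SAP text is still wrong as it stands.

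**Conclusion.** The C3 definition is wrong as written: 0.033 for every patient with a reduction, and a unit mismatch by a factor of 30.4375/7 = 4.35 that would survive if only the date were corrected.

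The last-dose grouping carries a real time-on-treatment selection in ORR, DCR, CBR, DOR and PFS; TTR is little affected. If reduction is unrelated to prognosis, the selection tends to favour the reduced-dose groups with no dose effect at all. At an assumed 9-month median PFS the 60-versus-20 mg gap in PFS is about 2 to 5 months for early reductions and more for later ones. It shrinks, and can reverse, with worse prognosis among reduction-prone patients or frequent re-escalation. Replacing the grouping is a cheap improvement to a descriptive analysis. It does not bear on the validity of the primary result.

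**What to change.** **C3.** Define time to first dose reduction in weeks as (date of first reduced dose − date of first dose + 1)/7, for patients with a reduction. Check that the separate derivation rules agree. This is a one-line change.

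**SAP 6.7.** Replace the last-dose grouping with a prespecified week-12 landmark comparison of 60 mg versus any reduced dose (40 and 20 mg pooled) among patients still progression-free. Class each patient by the last prescribed dose level at the landmark, including those on hold, and list those permanently off drug separately. If the last-dose table is kept, drop PFS and DOR from it, list the dose held when response was first seen, and footnote that the groups are defined by post-baseline dose history and do not support a dose comparison.

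**Cost.** Wording and programming on data already collected, but the landmark has limits:
- Week 12 is 84/30.4375 = 2.76 months. At median PFS 6 to 12 months it excludes 1 − 0.5^(2.76/6) = 27% down to 1 − 0.5^(2.76/12) = 15% of patients.
- Of 80 patients, about 41 to 50 remain at 60 mg and 16 to 20 at a reduced dose, only 2 to 4 of them at 20 mg, which is why the reduced doses are pooled. These counts come from the lead case and the later-reduction scenarios.
- With 41 versus 17 or 50 versus 20 patients and 60% to 80% events, exp(1.96·√(1/d1 + 1/d2)), where d1 and d2 are the event counts in the two groups, gives a 95% CI factor of about 1.8 to 2.1 either side of a hazard ratio. For an ORR difference, 1.96·√(0.25/n1 + 0.25/n2), with n1 and n2 the group sizes, gives 26 to 28 points. The result is descriptive only.
- Landmark ORR is about 60% to 70% in both groups, because early progressors are excluded, and must not be read against 52% or 30%.
- Confounding by prognosis remains. With reduction-prone patients at a hazard ratio of 0.75 or 1.33, lead-case post-landmark medians (60 mg versus reduced) are 9.4 versus 12.1 or 8.6 versus 6.8 months, with no dose effect.

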#### 7 INTERIM ANALYSIS

No interim analysis is planned.

#### 8 CHANGES IN THE PLANNED ANALYSIS

No changes are identified at this point.

**APPENDIX** 

10

#### 10.1 IMPUTATION OF PARTIAL DATES FOR AES/MEDICATIONS/THERAPIES/PROCEDURES

# IMPUTATION FOR AES WITH MISSING OR PARTIAL DATES

If AE start/end date are missing or partial missing, the following imputation rules apply.

- If end date of an adverse event is partially missing, impute as follows:
  - If both month and day are missing, then set to December 31
  - If only day is missing, then set to last day of the month
  - If the imputed end date > death date, then set to death date

If year of the end date is missing or end date is completely missing, do not impute.

If start date of an adverse event is partially missing, impute as follows:

- If both month and day are missing and year = year of treatment start date, then set to treatment start date
- If both month and day are missing and year ≠ year of treatment start date, then set to January 01
- If day is missing and month and year = month and year of treatment start date, the set to treatment start date
- If day is missing and month and year ≠ month and year of treatment start date, the set to first of the month

If year of the start date is missing or start date is completely missing, do not impute.

If the imputed start date > death date, then set to death date. If the imputed start date > the end date (or the imputed end date), set the imputed start date = end date (or the imputed end date).

# IMPUTATION FOR MEDICATIONS/THERAPIES/PROCEDURES WITH MISSING OR PARTIAL DATES

When the start date or end date of a medication/therapy/procedure is partially missing, the date will be imputed to determine whether the medication/therapy/procedure is prior or concomitant. The following rules will be applied to impute partial dates for medication/therapy/procedure:

If start date of a medication/therapy/procedure is partially missing, impute as follows:

- If both month and day are missing, then set to January 01
- If only day is missing, then set to the first of the month
- If the imputed start date > death date, then set to death date

If end date of a medication/therapy/procedure is partially missing, impute as follows:

- If both month and day are missing, then set to December 31
- If only day is missing, then set to last day of the month
- If the imputed end date > death date, then set to death date

Version 1.1: 02/28/2020 Page 26 of 28

• For prior anticancer therapy, the imputed end date should be the first dose date – 15 at the latest after imputation.

If the year of start date or year of end date of a medication/therapy/procedure is missing, or the start date or end date is completely missing, do not impute.

For detailed imputation rule for new anti-cancer therapy and death date, etc., please refer to a separate document "Standard Definitions and Derivation Rules of Key Variables V1".

#### 10.2 PRE- AND POST- PROTOCOL AMENDMENT (PA) HEMATOLOGICAL ANALYSES

The following safety data is considered for this analysis of comparison between pre- and post-PA:

# C1. Summary of Hematology Laboratory Values

The hematological laboratory values at baseline will be summarized descriptively. The incidence of abnormal hematology values at baseline and any postbaseline visits, and number of patients (%) with shifts in hematology results of  $\geq 2$  toxicity grades from baseline to worst postbaseline grade will be summarized. The hematological laboratory parameters (unit) of interest for these summaries are: Hemoglobin (g/L), Leukocytes (10^9/L), Lymphocytes (10^9/L), Neutrophils (10^9/L), Platelets (10^9/L).

